### o IES-R

Referring to the questionnaire in endpoint 32a, we calculate two different types of endpoints: continuous and binary.

Three different subscales are calculated from the questionnaire:

- Intrusion (item no. 1,3,6,9,14,16,20)
- Avoidance (item no. 5,7,8,11,12,13,17,22)
- Hyperarousal (2, 4,10,15,18,19,21)

The subscale values result from the addition of corresponding item values. The total score is then the sum of the subscales. This is a continuous endpoint.

For the diagnostic interpretation, X is calculated with the following formula:

X = (-0.02 x intrusion) + (0.07 x avoidance) + (0.15 x hyperarousal) - 4.36

A score X > 0 is then interpreted as suspected post-traumatic stress disorder, resulting in a binary variable.

For the IES-R questionnaire no missing items are allowed.

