### WHO-QoL German Version

The WHO-QoL questionnaire (30) is divided into six different subscales (sensibility, autonomy, past, social part, death and intimacy). The raw scores of the six subscales are formed by calculating the mean value of the items and multiplying by the factor 4. Each subscale value is then transformed to the range 0-100. The total score value is formed by calculating the mean of all subscale values. Only a maximum of one missing value per subscale is allowed (replaced by the mean of the resulting items), otherwise a missing is given.

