### o QUALIDEM (Dichter et al. 2016)

The QUALIDEM questionnaire (endpoint 30) is divided into different subscales. In our study, we evaluate the total score. This results from the addition of the item values. It must be taken into account that the positively directed items are scored inversely to the negatively directed items. This means that the answer option "Never" corresponds to a score of zero for a positively directed item and a score of six for a negatively directed item. No missing items are allowed.

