### o HADS-D

The HADS-D questionnaire (32b) is divided into two different subscales (anxiety and depression). The raw scores of the two subscales are formed by summing up the items. The total score is formed by the sum of the two subscale scores. A maximum of one missing item per subscale can be replaced by the rounded-up mean of the 6 available answers. In case of more missing items the score is missing.

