### 5.3 Missing data

The number of available observations and the number of missing observations of each variable will be presented for the intervention and control group separately, as well as for the total sample. All data will be analysed in an ITT approach.

The main analysis strategy is using all available data of all randomized NHs (full analysis set, FAS). For the primary endpoint (and all secondary endpoints related to DC1) no missing data is expected due to the nature of aggregated data collection.

For the unlikely situation of a substantial rate of missing values (>5%) in the primary outcome, a multiple imputation using chained equations will be applied in the ITT population for a sensitivity analysis. We will follow the recommendations of White, Royston and Wood (2011) in order to set up a proper imputation model assuming missing data to be missing at random (MAR). The imputation model includes simultaneously all above described variables (primary and secondary endpoints) of the DC1 at all measured time points.

The number of imputations (M) will be defined by the percentage of missing values in at least one of those defined variables at all time points. If the assumption of M=100\*FMI (Largest Fraction of Missing Information) is fulfilled, at least 20 imputations will be performed.

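### One blank item discards the whole IES-R or QUALIDEM score, although the SAP prorates its other scales, and DC2 scores have no fallback

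*SAP*

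**What the plan says.** SAP 1.2.3 sets the scoring rules for each questionnaire.

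- **IES-R (32a):** "For the IES-R questionnaire no missing items are allowed". The rule covers both the total score and the binary outcome X > 0.
- **QUALIDEM (part of 30):** "No missing items are allowed". Only the total score is evaluated.
- **WHO-QoL (the other part of 30):** "Only a maximum of one missing value per subscale is allowed", with mean replacement, over six subscales.
- **HADS-D (32b):** "A maximum of one missing item per subscale can be replaced", using the rounded-up mean of the other six answers.
- **ADBI (12):** up to two missing items for problem score #2 and one for the overall rating scale, with mean replacement. Problem score #3 also tolerates missing values.

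In SAP 5.3, "a multiple imputation using chained equations will be applied in the ITT population for a sensitivity analysis", but only if more than 5% of the primary outcome is missing, and the imputation model holds only DC1 variables. SAP 5.2 plans no sensitivity analysis for incomplete DC2 scores. SAP 5.4.3 would only extend the existing sensitivity analyses to other outcomes.

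SAP 5.1.3 analyses outcome 30 and the IES-R total as change from baseline. Secondary outcomes are exploratory, and neither 30 nor 32a is among the key ones (1.2.2).

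**The concern.** The difference in rules falls inside single outcomes. Within outcome 32, one blank on the HADS-D is repaired and one blank on the IES-R removes the score. Within outcome 30, a resident able to self-rate may have one missing item in each of six WHO-QoL subscales, while a resident assessed by QUALIDEM may have none. The SAP gives no reason.

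At stake is precision on trauma in relatives and on quality of life in residents who cannot speak for themselves. These data have already been collected, and any non-zero item non-response costs scores. If people who skip an item differ from those who do not, the remaining scores could also be unrepresentative.

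**Working it through.** **Inputs from the SAP.** The IES-R item lists in 1.2.3 hold 7 (intrusion), 8 (avoidance) and 7 (hyperarousal) items. 7 + 8 + 7 = 22, and items 1 to 22 each appear once. The stated maximum of 88 (1.2.2) gives 88 / 22 = 4 points per item, which fits scoring from 0 to 4. That scoring is inferred, since the SAP does not state it.

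**Assumptions.** The SAP gives no item non-response rate p and no number of QUALIDEM items. I vary p from 0.2% to 5%, with blanks independent across items, and take 20 to 40 items for QUALIDEM.

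**Formulas.**
- Strict rule, one time point: loss = 1 − (1 − p)^22.
- Strict rule, score needed at both t0 and t2: loss = 1 − (1 − p)^44.
- At most one blank per subscale: loss = 1 − A(7)² × A(8), with A(n) = (1 − p)^n + n p (1 − p)^(n−1).

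At p = 1%, the strict loss is 1 − 0.99^22 = 19.8%. For the tolerant rule, A(7) = 0.99797 and A(8) = 0.99731, so the loss is 1 − 0.99797² × 0.99731 = 0.7%.

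| p | Strict, one time | One per subscale, one time | Strict, t0 and t2 | One per subscale, t0 and t2 |
|---|---|---|---|---|
| 0.2% | 4.3% | 0.03% | 8.4% | 0.06% |
| 0.5% | 10.4% | 0.2% | 19.8% | 0.3% |
| 1% | 19.8% | 0.7% | 35.7% | 1.3% |
| 2% | 35.9% | 2.6% | 58.9% | 5.1% |
| 5% | 67.6% | 13.9% | 89.5% | 25.9% |

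The two right-hand columns apply to the change-from-baseline model, which as written needs a score at both times.

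**HADS-D for comparison.** Six available answers plus one missing implies 7 items per subscale. Under its own rule the HADS-D loses 0.4% at p = 1% and 1.6% at p = 2% (one time point).

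**QUALIDEM, strict rule, one time point.** With 20, 30 or 40 items the loss is 18.2%, 26.0% or 33.1% at p = 1%, and 33.2%, 45.5% or 55.4% at p = 2%.

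**Clustering.** At p = 1% a form has 22 × 0.01 = 0.22 blanks on average. The strict loss therefore cannot exceed 22%, when every blank falls on a different form. It can be as low as 1%, when all blanks come from forms left wholly empty. In that last case proration rescues nothing. Independence (19.8%) lies near the upper end.

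**Effect of one item on X.** The weights are −0.02, 0.07 and 0.15. If items score 0 to 4, one item can move X by at most 0.02 × 4 = 0.08 (intrusion), 0.07 × 4 = 0.28 (avoidance) or 0.15 × 4 = 0.60 (hyperarousal). X itself runs from −0.02 × 28 − 4.36 = −4.92 to 0.07 × 32 + 0.15 × 28 − 4.36 = 2.08. One intrusion item hardly matters, but one hyperarousal item can change the classification near the cut-off.

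**The case against.** The strict rule is clear, prespecified and the same in both arms, so it creates no difference between arms by itself. The two quality-of-life instruments are analysed separately. Rules that differ between instruments are not a contradiction: 1.2.3 says they follow the questionnaires, and QUALIDEM is tied to a cited manual that is not at hand. The SAP also has no single missing-item rule that could simply be extended. SAP 5.3 reports available and missing observations by group, so the loss would be visible. All of this stands. It limits the point to an improvement and makes the remedy conditional on the manuals, but it does not recover the discarded scores.

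A reader might infer that a large and selective share of scores will be lost. The SAP does not support this. It gives neither a non-response rate nor a pattern of blanks. If the scales are completed in interviews, which the SAP does not state, blanks may be rare. QUALIDEM is presumably completed by someone else, so its blanks need not follow the resident's frailty.

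Prorating X is also not harmless, as the 0.60 for one hyperarousal item shows. The binary outcome therefore needs separate handling.

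**Conclusion.** The point holds in a limited form. For IES-R and QUALIDEM the SAP discards nearly complete questionnaires for one blank, without a stated reason and with no imputation or sensitivity analysis for DC2 scores. Other scales in the same outcomes are prorated.

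The size is conditional. At one time point the IES-R loss runs from about 4% to 68% as assumed item non-response goes from 0.2% to 5%, and it is lower if blanks cluster. The QUALIDEM figures rest on an assumed item count as well. Selectivity remains a risk, neither shown nor excluded. The primary and key secondary results are untouched. This is a cheap improvement, not a threat to the trial's conclusion.

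**What to change.** - **IES-R total and QUALIDEM:** allow at most one missing item per subscale, replaced by the mean of that subscale's remaining items. For QUALIDEM, do this after item reversal, with the subscales taken from the cited manual because the SAP does not list them. If a scoring manual forbids proration, keep the strict rule and cite it as the reason. The SAP's reference list contains no scoring source for the IES-R.
- **Sensitivity analysis:** keep complete-item scoring for both scales.
- **Binary IES-R outcome (X > 0):** compute X from the prorated subscales and report the complete-item result alongside.
- **Reporting:** give, by arm, the number of returned questionnaires whose score is lost to blanks, separately from those not returned.

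The cost is a few sentences in 1.2.3 and 5.2 and one repeated run of each model. The downside is slight measurement error in the prorated scores. The change should be fixed before unblinding; if unblinding has already taken place, the prorated analysis should be labelled as added later.

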### WHO-QoL German Version

The WHO-QoL questionnaire (30) is divided into six different subscales (sensibility, autonomy, past, social part, death and intimacy). The raw scores of the six subscales are formed by calculating the mean value of the items and multiplying by the factor 4. Each subscale value is then transformed to the range 0-100. The total score value is formed by calculating the mean of all subscale values. Only a maximum of one missing value per subscale is allowed (replaced by the mean of the resulting items), otherwise a missing is given.

### o QUALIDEM (Dichter et al. 2016)

The QUALIDEM questionnaire (endpoint 30) is divided into different subscales. In our study, we evaluate the total score. This results from the addition of the item values. It must be taken into account that the positively directed items are scored inversely to the negatively directed items. This means that the answer option "Never" corresponds to a score of zero for a positively directed item and a score of six for a negatively directed item. No missing items are allowed.

### o HADS-D

The HADS-D questionnaire (32b) is divided into two different subscales (anxiety and depression). The raw scores of the two subscales are formed by summing up the items. The total score is formed by the sum of the two subscale scores. A maximum of one missing item per subscale can be replaced by the rounded-up mean of the 6 available answers. In case of more missing items the score is missing.

## 2 Study Methods

## 2.1 Trial design

BEVOR is a two-arm, parallel group, prospective, multicenter, cluster randomized controlled trial (cRCT). Nursing homes and related health care providers form the clusters and they themselves (DC1) or, respectively, their residents (DC2) the observation units. The allocation ratio of the clusters is 1:1 for the two groups:

- ACP program (experimental treatment group):
   Each nursing home and related care providers will receive an institutional and regional implementation of the complex German ACP program including a ACP facilitator .
- Care as usual (control group): For each nursing home and health care provider all common care options within the German health care system are available. The control group will receive a delayed ACP intervention after final data collection.

The trial is observer blinded (outcome assessors (until finalization of the SAP) and data collectors are blinded).

44 nursing homes with an average of 96 residents each, from the 4 study centres in Düsseldorf (2 regions), Munich (2 regions), Halle (2 regions) and Göttingen (2 regions) are participating.

### 2.2 Randomization

A 1:1 cluster-randomization at the level of NHs stratified by study center and region for experimental and control group was carried out using a computer-based code with variable block sizes with length 2 to 4 (to ensure intervention NHs in every region since it has been promised to the NHs) within each stratum. The randomization list was created by a research associate of the Institute for Medical Biometry and Epidemiology of the University Medical Center Hamburg-Eppendorf, who is not directly involved in the implementation of the research project using R version 3.6.2.

### 2.3 Sample size

To be allocated to trial: 44 NHs (22 per group) including on average n = 100 residents each, resulting in a target sample size of n = 4.400 (2.200 per group) enrolled patients in total.

To be analysed: n = 1760 residents in 22 NHs per group and n = 3520 residents in 44 NHs in total. Full details of sample size calculation can be found in the study protocol [2].

### 2.4 Framework

BEVOR is a cluster-randomized, prospective, parallel-group, superiority trial testing whether NHs involved in the structured ACP program will have a lower 12-month hospitalization rate than NHs in the control group.

### 2.5 Statistical interim analyses and stopping guidance

No interim analyses are planned.

## 2.6 Timing of final analysis

All endpoints (primary and secondary) are evaluated after collection of all data and the data cleaning process (i.e. database has been reviewed for completeness and accuracy), presumably December 2022 to March 2023.

The results will be reported according to the CONSORT 2010 Guideline [3].

Pooled descriptive analyses of data of both trial arms can be performed earlier, as soon as all data for this data collection is available, e.g. pooled baseline data of nursing homes (DC1) will be evaluated regardless of the intervention group after completion of the baseline DC1 data collection and the

corresponding data cleaning.

## 2.7 Timing of outcome assessments

The timeline of the BEVOR study is as follows (see Fig. 2 of the study protocol): at the start of the study, data collection is initiated, which corresponds with the baseline measurement (t0). At the end of the run-in phase of the intervention, the 12-month observation phase begins (t1). The end of the observation phase corresponds with the measurement at 12-months follow-up (t2). The run-in phase of the intervention describes the time in which the intervention is established and reaches the residents, the NHs and the regions. It lasts from the time of randomization until t1. The intervention itself continues during the observation period.

The 12 months observation period's data will be collected in one follow up collection (DC1) or, respectively, for DC2 continuously over the entire period, including

- interviews with relatives and nursing home staff of deceased residents,
- four three-monthly sessions to identify all potentially life-threatening events and related treatment decisions for the respective preceding 3 months (3CP data collection including interviews), as appropriate.

The start of the observation phase (t1) is fixed for all study centres at 01.09.2021.

**NH level (DC1):** All outcomes on NH level will be measured at t0, t1 and t2 for the preceding 12 months.

**Resident's level (DC2):** Data collection 2 is performed with residents, their surrogates and/or relatives, and the respective nursing staff and contains three different sections with different time points:

- 1. Framework survey including quality of care survey is conducted at t0 and t2 for the 12 months observation period.
- 2. Care consistency with care preferences (3CP) is assessed at t0 for the preceding 3 months and at t2. Data collection at t2 will be splitted into 4 phases of the 12-months observation period (each covering the preceding 3 months), beginning 3 months after t1, to collect data over the twelve months of observation as accurately as possible. It is ensured that there is no overlap in the survey periods.
- 3. The survey of relatives and staff regarding deceased residents is conducted at t0 and continuously over the 12 months before t2.

## 3 Statistical Principles

### 3.1 Confidence intervals and P values

All applicable statistical tests will be two-sided and at a 5% significance level. Analyses of secondary outcomes will be performed without adjustment for multiplicity. All confidence intervals presented will be 95% and two-sided.

## 3.2 Adherence and protocol deviations

Major protocol violation includes ineligible NHs and residents who were included in the trial by mistake, or for whom the intervention or other procedure differed from that outlined in the protocol, or failure of consent process.

Protocol violations are defined as deviations from the planned procedure according to the study protocol for which the study team is responsible. Major protocol deviations occur if

- the ACP facilitator does not attend the NH as scheduled
- data collection could not be performed (e.g. due to covid-19 pandemic)
- in- or exclusion criteria are violated (for both, residents and NHs)
- residents move out of the participating NH

Absence of sufficient adherence from the intervention according to the study protocol is defined at the NH and residents level. A major adherence deviation occurs if

- NHs of the intervention group do not utilize a minimum of the intervention elements (e.g. meetings of institutional steering group, staff qualification, ACP-facilitation, information of residents, relatives and surrogates), the minimum being defined as an intervention load amount below the respective median of all NHs in the intervention group

## 3.3 Analysis populations

### 3.3.1 Intention to treat Population (ITT)

The primary analysis population is the ITT (intention to treat) population. The ITT population on NH level consists of all NHs randomized to the study.

The ITT population on resident level consists of all enrolled residents who gave informed consent to participate in the study.

### 3.3.2 Per Protocol population (PP)

The Per Protocol population includes all NHs randomized (on NH) or all residents enrolled (on resident level) who have no major protocol violation (see 3.2).

More precisely, the per protocol population of NHs in the intervention group includes all NHs that meet the following criteria:

- Qualified interview facilitators were assigned to the NHs for the time of the intervention period
- Certification offers were made to the primary care physicians who cared for residents in the NHs belonging to the intervention group
- NHs were offered the intervention elements specified in the intervention concept

The per protocol population of NHs in the control group includes all NHs that were included and randomized according to protocol and did not violate any in- or exclusion criteria.

On resident level, the per-protocol population includes all residents of the PP NHs who did not move out of the participating NHs to another place of living before t2.

### 3.3.3 Adherence population

The adherence population includes all NHs randomized and all residents enrolled who are part of the respective PP populations and have no major adherence violation (see 3.2).

On NH level the intervention group of the adherence population includes all NHs with an intervention load as defined in 3.2 above the respective median of all NHs in the intervention group. A list of such NHs is provided to the Biometry by the interventionists after unblinding.

The adherence population of residents consists of all residents being part of the PP population who lived in adherent NHs.

## **4 Trial Population**

### 4.1 Screening data

The following summaries will be presented overall and by study centre: recruiting period, number of NHs screened, number of NHs and residents recruited, number of screened NHs, and residents not recruited.

### 4.2 Eligibility

The number of ineligible NHs will be reported, with reasons for ineligibility.

### 4.3 Recruitment

All recruitment information will be included and presented in a flow diagram according to the CONSORT Statement (extended version for cRCTs) (see Appendix).

The flow diagram summarizes the number of residents and/or NHs who

- meet the inclusion / exclusion criteria

- do not meet the inclusion/exclusion criteria
- post-hoc violate the inclusion / exclusion criteria
- are lost to-follow up
- have major protocol deviations
- died between t0 and t1
- are part of the ITT/PP population.

## 4.4 Withdrawal/follow-up

The number of residents/NHs dropping out of the study in the follow-up is documented as well as tabulated and will be given in the flow-chart. Dropout reasons will be given if known.

## 4.5 Characteristics of participating NHs and residents

The following descriptive characteristics are measured at t0 and, at NH level, additionally at t1:

### NH level:

- Type of owner
- Number of beds
- Occupied bed days (in the past 12 months)
- Number of residents (in past 12 months and on day of data collection) (respite & long term care)
- Sex ratio of residents
- Mean age of residents
- Rate of all deceased residents (in the past 12 months)
- Rate of registered/assistant/hired nurses per 100 residents
- Rate of full nurse equivalents per 100 residents
- Rate of palliative care qualified nurses per 100 residents
- Total sick leave days per nursing staff (i.e. number of registered/assistant/hired nurses) (in the past 12 months)
- Palliative care concept in place (yes vs. no)
- Active collaboration with palliative care services (yes vs. no)
- Collaboration with hospice care services (yes vs. no)
- Collaboration with ethic consultations (yes vs. no)
- Rate ethics consultations (in the past 12 months) per 100 residents
- Rate of general practitioners per 100 residents
- Defined private co-payment for residents (relative deviation from the regional mean)

### Residents level:

- Age
- Sex
- Country of birth
- Migration (yes vs. no)
- Professional degree
- Days since moving in at start of survey
- Insurance
- Marital status
- Religion
- Care level

